**Part C:**

Part C will consist of a 52-week period of reduced burden safety assessments, for subjects in the EU countries. Subjects can only enter Part C once they have entered and completed Part B. The Part B EOT will coincide with Part C Visit 1 for those subjects who are willing to continue with the 52-week reduced burden safety assessment period.

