**SCHEDULE OF EVENTS**  
**Part C EU Countries (Slovakia and Poland)**

	Part C 		EOT/ET	Follow-up Clinic Visit (ET Only)	Follow-up Call	Unscheduled	
Study Week →	After Amendment 07 Implementation 		52 Weeks after Part C V1	1 Week after ET	4 Weeks after Part C EOT/ET		
Visit Window (days)	+7	Part C V2, V3, V4 (q13 weeks) ±7 days	±7 days	±3 days	±3 days		
Activity Visit Type →	Part B EOT/Part C V1 	V	V	V	TC	V	TC
Informed Consent/Assent	X 						
Screening/ Demographics							
Inclusion/ Exclusion Criteria							
Update Medical History							
Vital Signs/ Weight 	X	X	X	X		X	
Physical Examination	X	X	X				
Complete Neurological Exam	X		X				
12-lead ECG	X	X	X			X 	
Blood Sampling for PK							
Chemistry/Hematology/UA	X						
Pregnancy Test 	U	U	U				
AIMS	X						
Video Recording of AIMS	X						
UPDRS Part III - Motor	X						
BARS	X						
HADS	X						
C-SSRS 	X	X	X	X		X	
ESS	X						
MoCA 	X						
Dispense Study Drug 	X 	X				X 	

	Part C 		EOT/ET	Follow-up Clinic Visit (ET Only)	Follow-up Call	Unscheduled	
Study Week →	After Amendment 07 Implementation 		52 Weeks after Part C V1	1 Week after ET	4 Weeks after Part C EOT/ET		
Visit Window (days)	+7	Part C V2, V3, V4 (q13 weeks) ±7 days	±7 days	±3 days	±3 days		
Activity Visit Type →	Part B EOT/Part C V1 	V	V	V	TC	V	TC
Assess Study Drug Accountability/ Compliance 		X	X				
Assess AEs	X	X	X	X	X	X	X
Assess Concomitant Meds	X	X	X	X	X	X	X
Evaluate Dyskinesia Control (subject/caregiver)	X						

SCHEDULE OF EVENTS (Part C) KEY

[figure not shown]
- [V] Clinic visit
- [TC] Telephone contact
- [EOT] End of Treatment
- [ET] Early Termination Visit
- [U] Urine pregnancy test for women of childbearing potential only

Abbreviations: AEs, adverse events; AIMS, Abnormal Involuntary Movement Scale; BARS, Barnes Akathisia Rating Scale; C-SSRS, Columbia Suicide Severity Rating Scale; ECG, electrocardiogram; ESS, Epworth Sleepiness Scale; EU, European Union; HADS, Hospital Anxiety and Depression Scale; MoCA®, Montreal Cognitive Assessment; PK, pharmacokinetics; q13 weeks, every 13 weeks; UA, urinalysis; UPDRS, Unified Parkinson’s Disease Rating Scale; V1, Visit 1.

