#### 3.1. Study Design

This is an open-label, single-arm study in which subjects with moderate to severe drug-induced TD who have successfully completed a parent study will be invited to participate. Successful completion of a parent study is defined as (1) study participation through Week 13; (2) the subject has generally been compliant with study drug and procedures, in the opinion of the investigator; and (3) the subject has no ongoing adverse events that are serious (serious adverse events)c, severe in intensity, or expected to interfere with their participation in this study.

Informed consent/assent (Part A) will be obtained before any study procedures are performed. Subjects may have informed consent/assent obtained up to 30 days in advance of subject's parent study Week 13 Visit/TD-Long Term Safety (LTS) Baseline Visit. Subjects who meet the selection criteria will be eligible to participate.

Informed consent/assent for Part B will be obtained after Amendment 06 implementation and before any study procedures related to Part B are performed.

Informed consent/assent for Part C will be obtained after Amendment 07 implementation and before any study procedures related to Part C are performed. Subjects who do not sign the informed consent/assent for Part C will complete the study at Part B Follow-up Call.

Subjects who have successfully completed a parent study may be eligible to rollover directly into this study after they complete a 1-week washout period and the Week 13 evaluation of the parent study. To reduce subject burden, after obtaining informed consent/assent, some data collected in the parent study will be used in the SD-809-C-20 study and will provide some of the baseline data for SD-809-C-20 (see [Schedule of Events](#)). In addition to assessments completed for the parent study Week 13 visit, evaluations required as part of the SD-809-C-20 study will be completed on the same day as the Week 13 visit.

---

c See Section 7 for evaluation of AEs with regard to severity, relationship to study drug, and definition of SAE.

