#### **Part C:**

For the EU countries, the study will include a reduced burden safety assessments period (Part C) of 52 weeks for subjects willing to continue in the study and who have completed Part B.

Subjects will continue treatment with SD-809 at the current dose administered during the 12-week open-label period of Part B. Subjects will be scheduled to return every 13 weeks ( $\pm 1$  week) until EOT. A follow-up clinic visit will occur 1 week after ET and a follow-up telephone call will occur 4 weeks after EOT/ET.

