## **6.6. Post-Treatment Safety Follow-up**

Following discontinuation of study drug at the Week 158 visit in Part A, subjects will have a clinic visit at Week 159 for evaluation of safety, dyskinesia, and motor function and a telephone contact at Week 162 for review of adverse events and concomitant medication use since Week 159.

Following discontinuation of study drug at the ET visit in Part A, subjects will have a clinic visit 1 week later for evaluation of safety, dyskinesia, and motor function and a telephone contact 4 weeks after the last dose for review of adverse events and concomitant medication use since ET.

Following discontinuation of study drug at the EOT visit in Part B, subjects will have a telephone contact 4 weeks after the last dose of study drug to evaluate the adverse events and concomitant medication use since EOT, unless they will continue with Part C.

Following discontinuation of study drug at the ET visit in Part B, subjects will have a clinic visit 1 week later for evaluation of safety, dyskinesia, and motor function and a telephone contact 4 weeks after the last dose of study drug to evaluate the adverse events and concomitant medication use since ET.

During the first week after stopping study drug, subjects should not take prohibited concomitant medications. Between the Week 158, EOT, or ET visit and the follow-up telephone contact, concomitant medication use is per the discretion of the Investigator.

Subjects in Part C who complete the 52 weeks of reduced burden safety assessments period will complete a Part C EOT Visit and a follow-up telephone contact 4 weeks after the last dose of study drug, to evaluate the adverse events and concomitant medication use since Part C EOT.

Subjects who discontinue study drug in Part C will complete an ET visit, a follow-up clinic visit 1 week later for safety evaluation, and a follow-up telephone contact 4 weeks after the last dose of study drug to evaluate the adverse events and concomitant medication use since ET.

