**Part A and B Combined:**

Some analyses, such as the analyses of adverse events, will be performed by time period. For these analyses, the following definitions will be used:

- Titration Period - from the first dose of treatment until 7 days after the week 6 visit. If a patient discontinues treatment before 7 days after the week 6 visit, then the Titration Period is until the last dose of treatment.
- Maintenance Period - from 8 days after the week 6 visit until the day of the week 158 visit for patients only in Part A and until the day of the open-label treatment EOT visit for patients in both Parts A and B. If a patient enters the Maintenance Period but discontinues treatment early, the Maintenance Period is until the last dose of treatment.

- Overall Treatment Period - includes the Titration and the Maintenance Periods, if applicable.
- Follow-up Period - from the end of the Overall Treatment Period through the end of the study.

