#### **5.1.2. Patient Disposition**

Patients in the ITT population, patients in the ITT population but not treated, patients in the safety population, patients in the randomized withdrawal ITT and randomized withdrawal mITT populations, patients who completed Parts A and B and the study, patients who withdrew from Parts A and B and the study, and patients who enrolled in Part C will be summarized using descriptive statistics. Patients who withdrew from Parts A and B and the study will also be summarized using descriptive statistics by reason for withdrawal.

The Part A visit when patients enrolled in Part B will be summarized using descriptive statistics.

Patients reaching each Part A visit will be summarized using descriptive statistics.

Reasons for withdrawal by Part A visits using the categories prior to week 54 visit, week 54 visit to before week 106 visit, and week 106 visit to before week 145 visit will be summarized using descriptive statistics.

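### Does the open-ended Follow-up Period in SAP 4.5 put on-drug Part C adverse events into the post-treatment AE table?

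*SAP*

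**What the plan says.** SAP 4.5, under the heading Part A and B Combined, sets the periods used for AE tables. For patients who entered Part B, the Maintenance Period runs "until the day of the open-label treatment EOT visit for patients in both Parts A and B", or to the last dose if treatment stops early. Titration plus Maintenance make up the Overall Treatment Period. The last bullet is "Follow-up Period - from the end of the Overall Treatment Period through the end of the study". SAP 7.1.3 then asks for an all-AE table for each of titration, maintenance and follow-up.

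The protocol joins Part C directly to Part B. The synopsis states: "The Part B EOT will coincide with Part C Visit 1 for those subjects who are willing to continue". Section 3.1 states: "Subjects will continue treatment with SD-809 at the current dose administered during the 12-week open-label period of Part B". The Part C schedule puts the end-of-treatment visit at "52 Weeks after Part C V1". Section 6.6 plans the call four weeks after Part B treatment "unless they will continue with Part C", and section 3.1 adds: "Subjects who do not sign the informed consent/assent for Part C will complete the study at Part B Follow-up Call".

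SAP 5.1.2 plans a disposition table in which "patients who withdrew from Parts A and B and the study, and patients who enrolled in Part C will be summarized".

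**The concern.** Taken link by link, the text seems to misfile data. The treatment period closes at Part B end of treatment. For a Part C entrant that is also the first Part C visit, drug continues, and the off-drug call is not made. Only patients who decline Part C finish the study at that call, so for an entrant the end of the study comes later. AEs are collected to the final study visit (Protocol section 7). SAP 5.1.2 also names the study separately from Parts A and B, so the end of the study cannot simply be equated with the end of Part B.

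At stake is the meaning of the follow-up table. A reader takes it as the record of events after SD-809 is stopped. If it held events from patients still on drug, it would describe neither state cleanly, and the same events could appear again in Part C reporting.

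A smaller point goes with it. SAP 2.2.1 lists counts of patients over QTcF thresholds as a Part B endpoint, but SAP 7.2.6 plans only normal/abnormal shifts, and SAP section 9 does not declare the omission. The combined counts in SAP 7.1.7 are post-baseline, so they can include ECGs taken at the end of the placebo week.

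**Working it through.** The SAP gives no figure to reproduce here. The check is one of text, with short arithmetic for the size.

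**1. Literal window, using the Part C schedule of events**
- Part C completer: 52 × 7 + 4 × 7 = 364 + 28 = 392 days, or 56 weeks. With ±7 days on the Part C end-of-treatment visit and ±3 on the call: 382 to 402 days.
- Any other patient: 4 × 7 = 28 days, or 25 to 31 with ±3 days on the call.
- The completer's window is a ceiling. SAP 2.5.3 runs the analysis once the last Part B patient finishes Part B, and neither document shows that any entrant has completed Part C by then. On-drug time inside the literal window at the cut is therefore between 0 and 52 weeks per entrant.
- Actual Part C enrolment is not given; the protocol plans about 102. As an assumption, 25, 51 or 102 entrants who all complete 52 weeks give n × 364/365.25 = 24.9, 50.8 or 101.7 patient-years. These too are ceilings. The number of events cannot be derived.

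**2. Which scope governs the sentence**
- The bullet's own heading restricts the definitions to Parts A and B.
- SAP 7.1.1 makes that the default for the safety summaries, and the follow-up table is one of them. Nothing in 7.1.3 notes otherwise.
- SAP 2.5.3 describes the final analysis as that of Parts A and B.
- Protocol 8.4 gives Part C its own AE endpoint, counted from the start of Part C.

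Under that scope a Part C entrant has 0 weeks of Parts A and B follow-up. This agrees with Protocol 6.6, which plans no call for these patients. The shared visit day is settled as well: Maintenance includes the day of the Part B end-of-treatment visit.

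**3. Consistency**
The duration formula in SAP 7.1.2 (last day of drug minus first day plus 1) also carries no Part C limit, yet it is naturally read as exposure in Parts A and B. The same reading bounds Follow-up. The top exposure category in 7.1.2 does not help either way. The longest course through Parts A and B is 158 + 1 + 12 = 171 weeks, but the category is 171 weeks or more and so has no upper end.

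**4. What a literal reading would touch**
Only the follow-up AE table. The event rate, Kaplan-Meier censoring and exposure-adjusted rates in SAP 7.1.3 are each limited in words to treatment in Parts A and B. The Part A AE endpoint in SAP 2.2.1 names overall, titration and long-term treatment, not follow-up.

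**5. QTcF**
The threshold counts in SAP 7.1.7 are not restricted to Part A visits, and 7.1.1 makes them Parts A and B combined. Part B exceedances are therefore counted, though not by randomized arm. Off-drug contamination is one scheduled ECG per placebo patient, at the Post-withdrawal Visit. It alters a patient's classification only if a threshold is crossed there and at no other post-baseline ECG.

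**The case for a change.** The best case for a change is that the SAP writes a Parts A and B limit where it wants one (event rate, censoring, exposure-adjusted rate) and wrote none in the Follow-up bullet. A heading and a general scope rule give no end date, so a programmer has to infer it. The SAP introduction says the SAP prevails over the protocol where they differ, which weakens any appeal to Protocol 8.4. Patients who finished Part B early may already have Part C events at the cut. One clause would remove the doubt.

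What stands is that the sentence does not state the cut-off. The rest does not carry far. The heading, 7.1.1 and 2.5.3 are all in the SAP, so the scope does not depend on the protocol, and read within that scope the two documents do not differ. Counting Part C enrolment in SAP 5.1.2 needs only enrolment status; it does not bring Part C AE records into these tables. A clause would record the cut-off that the scope already implies, which table specifications can do equally well.

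The QTcF mismatch between SAP 2.2.1 and 7.2.6 also stands as an undeclared omission. It concerns a descriptive count over a one-week period whose exceedances already enter the combined table.

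**Conclusion.** No change is needed. The Follow-up bullet leaves out a detail that its own heading and the SAP's scope rule supply, and analysts would fill it the same way: no Parts A and B follow-up time for a patient once Part C begins. On that reading the number of misplaced events is zero.

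On the literal reading, the exposure is one descriptive AE table and 0 to 52 on-drug weeks per Part C entrant, with the number of entrants and events unknown. No inferential result, treatment-period AE table, rate or time-to-event display depends on it. The QTcF point is a listing mismatch with at most one scheduled off-drug ECG per placebo patient, and no conclusion turns on it.

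This rests on two assumptions: that the programming follows SAP 7.1.1, and that Part C events are reported separately, as Protocol 8.4 provides.

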## **5. STUDY POPULATION**

### **5.1. Part A**

#### **5.1.1. General**

The ITT population will be used for all study population summaries. Summaries will be presented by parent study treatment group (prior SD-809 and prior placebo) and overall.

#### **5.1.2. Patient Disposition**

Patients in the ITT population, patients in the ITT population but not treated, patients in the safety population, patients in the randomized withdrawal ITT and randomized withdrawal mITT populations, patients who completed Parts A and B and the study, patients who withdrew from Parts A and B and the study, and patients who enrolled in Part C will be summarized using descriptive statistics. Patients who withdrew from Parts A and B and the study will also be summarized using descriptive statistics by reason for withdrawal.

The Part A visit when patients enrolled in Part B will be summarized using descriptive statistics.

Patients reaching each Part A visit will be summarized using descriptive statistics.

Reasons for withdrawal by Part A visits using the categories prior to week 54 visit, week 54 visit to before week 106 visit, and week 106 visit to before week 145 visit will be summarized using descriptive statistics.

#### **5.1.3. Demographics and Baseline Characteristics**

The continuous variables of patient age, weight, height, and body mass index (BMI), all collected at baseline in the parent study, will be summarized using descriptive statistics. The categorical variables of patient sex, race, ethnicity, and education ( $\leq 12$  or  $> 12$  years) (collected at baseline in the parent study) will be summarized using descriptive statistics for each category. Missing categories will be presented if necessary.

The continuous variables of time since tardive dyskinesia diagnosis in years, baseline total motor AIMS score, and baseline mCDQ-24 total score, all determined from baseline in the parent study, will be summarized using descriptive statistics. The categorical variables of baseline use of DRA (Yes/No), background comorbid illness types, use of a strong CYP2D6 inhibitor (Yes/No), poor CYP2D6 metabolizer (Yes/No), and impaired CYP2D6 function (Yes/No), all determined from baseline in the parent study, will be summarized using descriptive statistics for each category.

Strong CYP2D6 inhibitor status was determined by classifying patients as taking versus not taking a strong CYP2D6 inhibitor (paroxetine, fluoxetine, or bupropion) at baseline in the parent study. Impaired CYP2D6 function was defined as use of a strong CYP2D6 inhibitor at baseline in the parent study and/or a poor CYP2D6 metabolizer.

#### **5.1.4. Prior Medications**

All prior medications will be coded using the World Health Organization dictionary of medical codes (WHO Drug). The incidence of prior medications will be summarized using descriptive statistics by therapeutic class and preferred term. The therapeutic class will be displayed as the ATC3 code if available or the most specific ATC code if ATC3 is not available. The preferred term is displayed as the collapsed preferred term (single generic ingredients collapsed to base substance preferred term). Patients are counted only once in each therapeutic class category, and only once in each preferred term category. Prior medications will include all medications taken prior to the first day of study drug treatment.

#### **5.1.5. Protocol Deviations**

Patients with at least 1 protocol deviation as recorded on the CRF, and protocol deviations for each category will be summarized using descriptive statistics.

### **5.2. Part B**

#### **5.2.1. General**

The randomized withdrawal ITT population will be used for all Part B study population summaries. Summaries will be presented by randomized withdrawal treatment group (SD-809 and placebo) and overall.

#### **5.2.2. Patient Disposition**

Patients in the randomized withdrawal ITT and randomized withdrawal mITT populations, patients who completed Part B, and patients who withdrew during Part B will be summarized using descriptive statistics. Patients who withdrew during Part B will also be summarized using descriptive statistics by reason for withdrawal.

#### **5.2.3. Demographics and Baseline Characteristics**

The continuous variables of patient age, weight, and body mass index (BMI) (all collected at the Pre-Withdrawal Visit, and height (collected at baseline in the parent study) will be summarized using descriptive statistics. The categorical variables of patient sex, race, ethnicity, and education ( $\leq 12$  or  $>12$  years) (collected at the Pre-Withdrawal Visit) will be summarized using descriptive statistics for each category. Missing categories will be presented if necessary.

The continuous variables of time since tardive dyskinesia diagnosis (calculated at the Pre-Withdrawal Visit) and pre-withdrawal total motor AIMS score will be summarized using descriptive statistics. The categorical variables of pre-withdrawal use of DRA (Yes/No), pre-withdrawal use of CYP2D6 inhibitors, and pre-withdrawal use of a strong CYP2D6 inhibitor (Yes/No) will be summarized using descriptive statistics for each category.

Strong CYP2D6 inhibitor status was determined by classifying patients as taking versus not taking a strong CYP2D6 inhibitor (paroxetine, fluoxetine, or bupropion) at the Pre-Withdrawal Visit.

## **6. EFFICACY ANALYSIS**

### **6.1. Part A**

#### **6.1.1. General**

The ITT population will be used for all efficacy summaries. Summaries will be presented by parent study treatment group and overall for Part A visits.

All continuous efficacy endpoints will be summarized for actual values and changes (or percent changes) from baseline of this study to each visit using descriptive statistics.

All categorical efficacy endpoints will be summarized at each visit using descriptive statistics. In addition, the CGIC and PGIC ratings at each visit will be summarized using descriptive statistics.

The mCDQ-24 domain scores will also be summarized for actual values and changes from baseline of this study to each visit using descriptive statistics.

No inferential statistics will be presented for efficacy endpoints.

### **6.2. Part B**

#### **6.2.1. General**

The randomized withdrawal mITT population will be used for the efficacy analysis in Part B. The summaries will be presented by randomized withdrawal treatment group and overall, unless otherwise noted.

#### **6.2.2. Efficacy Variables and Analyses**

The primary efficacy variable is the change in total motor AIMS score as assessed by blinded central video rating from Pre-Withdrawal Visit to Post-Withdrawal Visit

Analysis of the change in total motor AIMS score as assessed by blinded central video rating during the Randomized Withdrawal Period (from the Pre-Withdrawal Visit to the Post-Withdrawal Visit) will use an analysis of covariance (ANCOVA) model with the change in total motor AIMS score as the dependent variable. The model will include randomized withdrawal treatment group and DRA status at the Pre-Withdrawal Visit as fixed effects, and the total motor AIMS score at the Pre-Withdrawal Visit value as a covariate. The least squares means of the change in total motor AIMS score will be compared between the SD-809 treatment and placebo groups using a 2-sided test at the  $\alpha=0.05$  level of significance. The SAS code for this test is as follows:

[REDACTED]

The least square (LS) mean and standard error for the treatment groups, and the LS mean difference, 95% confidence interval (CI), and p-value for the comparison (SD-809 vs. placebo) will be presented at the Post-Withdrawal Visit.

Total motor AIMS score values (central reading) and changes from the Pre-Withdrawal Visit to the Post-Withdrawal Visit and EOT visit will be summarized using descriptive statistics for each treatment group. The overall summary will not be presented at the Post-Withdrawal Visit.

In addition, total motor AIMS score (site rating) values and changes from the Pre-Withdrawal Visit to the Post-Withdrawal Visit and EOT visit will be summarized using descriptive statistics for each treatment group. The overall summary will not be presented at the Post-Withdrawal Visit.

